12.3.1 Reporting Requirements and Timelines for Adverse Events and Device Deficiencies

All AEs and DDs need to be reported in a timely manner to the sponsor and to the IRB/EC per the IRB/EC reporting requirements. It is the responsibility of the investigator and the sponsor to abide by the AE and DD reporting requirements as stipulated by local law and the study site's IRB/EC.

Туре:	Report to:	Reporting Timeframe (from time of learning of event):
DD	Sponsor	Recommended within 10 working days
	IRB/EC	Per IRB/EC reporting requirements
AE	Sponsor	Recommended within 10 working days
	IRB/EC	Per IRB/EC reporting requirements
SAE	Sponsor	Recommended within 10 working days
	IRB/EC	Per IRB/EC reporting requirements
ADE	Sponsor	Recommended within 10 working days
	IRB/EC	Per IRB/EC reporting requirements
SADE	Sponsor	Recommended within 10 working days
	IRB/EC	Per IRB/EC reporting requirements

Table 6: Reporting Requirements Timeframe for Investigators

12.4 Reporting of Adverse Events and Device Deficiencies

Investigators should assess and report the appropriate information on the AE eCRF for the following events, starting from the point of skin incision until the subject exits the study:

- o All AEs related to the MaxTack[™] Motorized Fixation Device, mesh, or study procedure
- o All events that lead to death, regardless of relatedness
- Any non-subject adverse event

Reporting requirements are noted in Section 12.3.1. Assessment of events will include date of event, relationship to study device, relationship to mesh, relationship to study procedure, description, seriousness, action(s) taken, date of resolution and outcome. Additionally, any medication/treatment administered to resolve an AE must also be reported.

Subject Status AE Reporting		AEs to Report Timeframe		
	Required			
Preoperative Screen failure	No	N/A		
Intraoperative Screen failure	No	N/A		
Enrolled	Yes	From skin incision through Study Exit (e.g., study completion, withdrawal or LTFU)		

 Table 7: Subject Status Adverse Event Reporting

12.4.1 Adverse Event and Device Deficiency Classification

All AEs and DDs will be reviewed by a Medtronic representative. AEs and DDs will be classified according to the definitions provided.

Upon receipt of an AE, a Medtronic representative will review the AE/DD for completeness and accuracy and when necessary, will request clarification and/or additional information from the Investigator. Medtronic will utilize Medical Dictionary for Regulatory Activities (MedDRA) for Regulatory Activities, to assign a MedDRA term for each AE based on the information provided by the investigator.

Regulatory reporting of AEs and DDs will be completed according to local regulatory requirements. Refer to Table 6 for a list of site reporting requirement timeframes. It is the responsibility of site and Medtronic to abide by any additional AE reporting requirements stipulated by the IRB/EC responsible for oversight of the study.

AFFIX (MaxTack [™] Motorized Fixation Device) Clinical Investigation Plan				
MDT23014	Revision	3.0	Page 55 of 97	Medtronic

Table 8: Adverse Event and Device Deficiency Classification Responsibilities

What is classified?	Who classifies?	Classification Parameters
Relatedness	Investigator	MaxTack [™] Device, mesh, study procedure
Relateuriess	Sponsor	MaxTack [™] Device, mesh, study procedure
Seriousness	Investigator	SAE, DD with SADE potential
Senousness	Sponsor	SAE, DD with SADE potential
Diagnosis	Investigator	Based on presenting signs and symptoms and other supporting data
Diagnosis	Sponsor	MedDRA term assigned based on the data provided by Investigator

Appendix I contains the Foreseeable Adverse Event List (FAL), which is a list of AEs related to the device or procedure that have been observed in previous studies and may be experienced by subjects.

12.5 Processing Updates and Resolution

For any changes in status of a previously reported AE or DD (i.e., change in actions taken, change in outcome, change in relatedness), information needs to be updated, or added to the original AE or DD eCRF. All AEs must be followed until the AE has been resolved, is unresolved with no further actions planned, the subject dies or exits the study, or until study closure, whichever occurs first.

In the event that a subject is exited from the study, all efforts should be made to continue following the subject until all unresolved device or study procedure related AEs, as a classified by the investigator, are 'resolved', 'unresolved with no further actions planned', or the subject has been followed for 30 days, whichever occurs first after which the subject should be exited. If AEs are still ongoing 30 days post study completion, the subject will be exited and the AE eCRF updated to indicate the AE is unresolved.

At the time of study exit, all collected AEs that are 'unresolved' must be reviewed and an update to the original AE eCRF must be reported. Any AEs with outcomes classified as 'recovering/resolving', and where no update can be provided at the time of study exit, will be updated to 'not recovered/not resolved'.

12.6 Product Complaint Reporting

A product complaint is any written, electronic, or oral communication that alleges deficiencies related to the identity, quality, durability, reliability, safety, effectiveness, or performance of a medical device that has been placed on the market. It is the responsibility of the investigator to report all product complaint(s) associated with a medical device distributed by Medtronic, regardless of whether they are related to intended use, misuse, or abuse of the product. Reporting must be done immediately and via the regular channels for market-released products. The reporting of product complaints by the clinical team must be

	AFFIX (MaxTack [™] Motorized Fixation Device) Clinical Investigation Plan				
MDT23014	Revision	3.0	Page 56 of 97	Mectronic	

done according to the local Standard Operating Procedures and Medtronic will notify the RAs as applicable or the following incidents immediately upon learning of them:

- Any malfunction or deterioration in the characteristics and/or performance of a device, as well as any inadequacy in the labeling or instructions for use which led or might have led to the death or serious deterioration in the state of health of a patient, user, or other person.
- Any serious deterioration in the state of health related to the device or procedure, including:
 - Life-threatening illness or injury
 - Permanent impairment of a body function or permanent damage to a body structure
 - A condition necessitating medical or surgical intervention to prevent permanent impairment of a body function or permanent damage to a body structure

12.7 Subject Death

All subject deaths after the point of skin incision must be reported by the investigator to Medtronic on an AE eCRF (AE with outcome of fatal) as soon as possible after the investigator or delegated member of the study team first learns of the death. In case of death, there should be one AE with the outcome of fatal.

A redacted copy of the death certificate, if available and allowed by state/local law, should be sent to the Medtronic clinical study team. When a death occurs in a hospital, a copy of the death summary report and all relevant hospital records, if available, should be sent to the Medtronic clinical study team. If an autopsy is conducted, a copy of the autopsy report should also be sent to the Medtronic clinical study team if available and allowed by state/local law. When a death occurs at a remote study site, it is the investigative study site's responsibility to attempt retrieval of information about the death. Additionally, device disposition information should be updated.

In summary, the following data will be collected (all documents should have Protected Health Information (PHI) redacted):

- Date of death
- Detailed description of death
- Relatedness to device and procedure
- Device disposition information
- Death summary/hospital records (if available and allowed by state/local law)
- Autopsy report (if available and allowed by state/local law)
- Death certificate (if available and allowed by state/local law)
- Any other relevant details as requested by Medtronic

	AFFIX (MaxTack [™] Motorized Fixation Device) Clinical Investigation Plan				
MDT23014	Revision	3.0	Page 57 of 97	Medtronic	

13. External Committees

13.1 Independent Medical Monitor

At regular intervals, an independent Medical Monitor (MM) will conduct an independent adjudication of specified adverse events for subjects participating in the study. Source documents to support adjudication may be requested.

The MM will be a board-certified/board-eligible physician with expertise in hernia surgery and experience in the use of similar tacking devices. This physician will not be employed by Medtronic, will not be a participating investigator in the study, and will possess the necessary qualifications through education, training, and relevant experience to oversee the product's use and associated procedures.

Most adjudications will be conducted independently by the MM via entry of their assessments into the database. Medtronic personnel may facilitate adjudication meetings if needed, but the final adjudication decision will be solely from the MM.

If the MM disagrees with the investigator's classification of the event, the MM assessment will be provided to the investigator. If the investigator agrees with the MM's adjudication, the investigator is responsible for updating the AE CRF accordingly.

If the investigator does not agree with the MM's adjudication classification, both determinations will be provided within the final report; however, the MM's adjudication will be used for data analysis. If required, both determinations will be included in reporting to IRB/ECs and regulatory authorities.

14. Statistical Design and Methods

This section presents statistical considerations and justification for the study design and provides a highlevel description of planned analysis and reporting. More details will be given in a separate Statistical Analysis Plan (SAP) that will be finalized and approved before first data freeze or lock. Any deviation to the prespecified statistical analyses including justification, will be noted in the clinical study report(s).

14.1 General Aspects of Analysis

Data analysis will be performed by Medtronic or its designee.

The primary analysis will be based on all evaluable subjects, which will utilize a performance goal (PG), as outlined in Section 14.4. The Clopper-Pearson exact method, along with a 95% confidence interval, will be used for statistical evaluation. A two-sided p-value less than 0.05 (one-sided less than 0.025) is considered statistically significant. Subject disposition will be illustrated in a CONSORT diagram.

The study will be considered successful if the upper 95% two-sided confidence limit for the proportion of hernia recurrence within 3-months is less than the performance goal of 8.6%. With an evaluable sample

AFFIX (MaxTa Clinical Invest				
MDT23014	Revision	3.0	Page 58 of 97	Medtronic

size of 100 or more, a rate of 3% (3 or less) hernia recurrence within 3-months will be required to meet the PG.

Descriptive statistics will be used to summarize study outcomes. Continuous variables will be summarized using means, standard deviations, quartiles, minimum, maximum values and 95% confidence intervals, as appropriate. Categorical variables will be summarized using counts, percentages and 95% confidence intervals, as appropriate.

Subject visits will be tabulated and compliance to visit schedule / visit windows will be summarized. The main analysis will include data from all study sites.

All statistical analyses will be performed using SAS for Windows (Version 9.4 or higher, SAS Institute Inc. Cary, NC), R Statistical Software (Version 4.2.1 or higher; R Core Team 2022), or other widely accepted statistical or graphical software.

14.2 Analysis Population

Statistical analysis for device performance (including primary and secondary endpoints) will be performed on the Full Analysis Set (FAS) as the primary analysis and on the Per Protocol Analysis Set (PPAS) as supportive analysis, as described in the Statistical Analysis Plan (SAP).

- Full Analysis Set (FAS): Including any subject enrolled and received study device (representing the primary analysis population)
- **Per Protocol Analysis Set (PPAS)**: Subset of Full Analysis Set excluding subjects in the following situation. Subject's data will be part of the PPAS until the following is reached:
 - o Tack removal
 - o Mesh removal or alteration (Mesh cut or partially excised during the procedure)
 - o Subject with protocol deviations that may impact performance outcome measurements

14.3 Analysis Execution

The primary analysis will be conducted when all subjects have completed their Month 3 follow-up visits (or exited the study) and may be used for regulatory and publication purposes. The final analysis for the study will occur when all study subjects have completed the Month 12 follow-up visit and/or exited the study, and a final report will be prepared. The analysis will include both primary and secondary endpoints. The primary objective is based on the hernia clinical recurrence rate within the 3-month follow-up and may be assessed prior to study completion for regulatory and communication needs. The study will continue through 12 months post-procedure to evaluate performance and safety.

AFFIX (MaxTa Clinical Invest				
MDT23014	Revision	3.0	Page 59 of 97	Medtronic

14.4 Primary Objective(s)

14.4.1 Primary Objective (Performance)

The primary objective of this study is to assess the performance of the MaxTack[™] Motorized Fixation Device in minimally invasive ventral hernia repair procedures by evaluating the hernia recurrence rate within 3 months. The primary outcome is hernia recurrence rate within 3 months by a Valsalva maneuver at a clinical exam and confirmed per site standard of care medical imaging, if necessary.

14.4.2 Rationale for Performance Criteria

The primary endpoint is defined in Section 5.2.1. The primary endpoint will be assessed in comparison to a performance goal (PG) based on meta-analysis of available literature ⁽¹³⁻²²⁾ (Figure 6). The estimated expected hernia recurrence rate within 3 months is 1.0% (95% CI: 0.6% to 4.6%). The PG for the study is set at 8.6% (Figure 6), which is based on the upper bound of the CI from the meta-analysis at 4.6% plus a 4% clinical margin to balance the number of subjects, account for variability of subjects treated in a real-world setting and maintain proof of acceptable performance.

The meta-analysis was done using R Version 4.2.1 ⁽¹²⁾. A random intercept logistic regression model was used to accommodate variations across studies and the bootstrap method was used to estimate the confidence interval for the average proportion $^{(23, 24)}$.

14.4.3 Hypothesis and Performance Requirements

The null and alternative hypotheses are as follows:

 H_0 : three-month recurrence rate \geq 8.6% versus

H₁: three-month recurrence rate <8.6%

[figure not shown]
The primary objective will be met if the upper 95% two-sided confidence limit for the hernia recurrence rate within 3-months is less than the performance goal of 8.6%.

14.4.4 Analysis Method

A binomial test for proportion with a one-sided alpha of 0.025 will be used on the FAS to test the hypothesis, and 95% two-sided Clopper-Pearson confidence intervals will be calculated. A sample size of approximately 110 is planned (100 evaluable, assuming 9% attrition). If three or less recurrences (3%) are observed out of 100, the performance goal will be met.

AFFIX (MaxTack [™] Clinical Investigati				
MDT23014	Revision	3.0	Page 60 of 97	Medtronic

Figure 6: Forest Plot for Meta-analysis of 3-Month Recurrence Rate for Ventral Hernia Surgeries done with Absorbable Tacks¹

14.5 Secondary Objective(s)

The secondary objective of this study is to evaluate the performance and safety of the MaxTack[™] Motorized Fixation Device when used for fixation in minimally invasive ventral hernia repair procedures within 12 months post procedure.

See Section 5.2.2 for a full list of secondary endpoints.

Where applicable, descriptive statistics and 95% confidence intervals will be used to summarize secondary study endpoints. Continuous variables are presented as means, standard deviations (SD), medians, first and third quartiles, and minimum/maximum and categorical variables as counts and percentages. A statistical summary of secondary endpoints will be based on data from the full analysis set for subjects, with non-missing data for each secondary endpoint. Recurrence endpoints will be based on a previous recurrence or evaluable data at the time point.

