5.2.2 Secondary Endpoints

The secondary endpoints will include:

- Incidence of Surgical Site Occurrence (SSO) which are the following Adverse Events (AEs) related to the study device, mesh, and / or study procedure and defined as Seroma, Hematoma, Surgical Site Infection (SSI), bleeding at tack implantation site following the MaxTack[™] Motorized Fixation Device used for fixation in minimally invasive ventral hernia repair procedures at the following timepoints:
 - by Discharge
 - o within 1 month
 - within 3 months
 - within 12 months
- Incidence of SSO requiring Procedural Intervention (SSOPI), which are the following AEs related to the study device, mesh, and/or study procedure and defined as Seroma, Hematoma, Surgical Site Infection, bleeding at tack implantation site following the MaxTack[™] Motorized Fixation Device used for fixation in minimally invasive ventral hernia repair procedures at the following timepoints:
 - by Discharge
 - o within 1 month
 - o within 3 months
 - o within 12 months
- Incidence of hernia recurrence following the MaxTack[™] Motorized Fixation Device used for fixation in minimally invasive ventral hernia repair procedures. The evaluation of hernia recurrence will be performed via a Valsalva maneuver during a physical examination and confirmed per site standard of care medical imaging, if necessary, at the following timepoints:
 - \circ within 1 month
 - o within 12 months
- Incidence of hernia recurrences resulting in reoperation, defined as an operative procedure performed with the specific goal of repairing the recurrent hernia, at the following timepoints:

- o within 1 month
- \circ within 3 months
- within 12 months
- Incidence of MaxTack[™] Motorized Fixation Device deficiencies (e.g., insufficient tack penetration, loose tacks, tack(s) migration, tacker issue battery etc.) on day of the index procedure.
- Operative time for mesh fixation, defined as the time elapsed from the initiation of the mesh fixation process with MaxTack[™] to its completion
 - Surgeon satisfaction as assessed by Surgeon Satisfaction Questionnaire postoperatively.
 - Length of hospital stay after minimally invasive ventral hernia repair procedure where the MaxTack[™] Motorized Fixation Device was used for fixation.
- Change in subject-reported pain at the hernia site evaluated with Numeric Rating Scale (NRS) score from 0 to 10 at screening and compared to the following timepoints:
 - o at Month 1
 - o at Month 3
 - o at Month 12

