 - Change in subject Quality of life (QoL), as measured through the administration of the Hernia Quality of Life Survey (HerQLes) questionnaire, evaluated at screening and compared to the following timepoints:
 - o at Month 1
 - o at Month 3
 - o at Month 12

6. Study Design

This prospective, post-market, multicenter, nonrandomized, single-arm, interventional clinical study will evaluate the performance and safety of the MaxTack[™] Motorized Fixation Device when used for fixation in minimally invasive ventral hernia repair procedures.

The study is expected to be conducted at approximately 10 study sites located in the United States (US). However, additional sites in other regions may be added as needed to meet study objectives. Approximately 110 subjects will be enrolled in the study using the MaxTack[™] Motorized Fixation Device. Enrolled subjects will be subjects who have signed an informed consent form, who meet all eligibility criteria and at least one MaxTack[™] tack is utilized for fixation. Study subjects will be evaluated at Screening (-60-0 days preoperative), Operative, Discharge, Month 1 (30-51 days postoperative), Month 3 (90-120 days postoperative), and Month 12 (365-410 days postoperative) visits.

Measures to control bias:

Enrollment parameters are included in the study to avoid introduction of bias to the study results due to disproportionate enrollment. Enrollment shall not exceed 25 subjects per site (this is 25% of the minimum

AFFIX (MaxTa Clinical Invest				
MDT23014	Revision	3.0	Page 24 of 97	Medtronic

number of evaluable subjects needed [100]). Enrollment will be competitive across study sites. The perstudy site enrollment cap may be increased upon sponsor approval. At any time, the study sponsor may place an enrollment hold on individual sites for reasons relating to data quality, overall performance, concerns with Principal Investigator (PI) oversight, or other reasons not specified within the Clinical Investigative Plan (CIP).

All investigators will be required to provide financial disclosure (FD). Physicians will not be able to participate if they have any significant conflict of interest that cannot be mitigated in this study.

Physicians performing procedures will be qualified surgeons experienced with hernia repair procedures.

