Surgical Site Occurrences (SSO) has been defined in this study as the following AEs: Seroma, Hematoma, Surgical Site Infection, and bleeding at tack implantation site. These events were chosen based on previous clinical studies and tailored to the type of events that could occur due to fixation, including tacks ⁽²⁵⁾. Though other events may occur in a subject, these SSOs (beyond hernia recurrence) are the events of interest for this study.

The visit windows for the Month 1, 3, and 12 visits all open on the target date (e.g., Month 1 window begins at 30 days) rather than the allowance for windows to open early. The visit windows are designed to ensure accurate capture of what occurred within that timeframe rather than evaluating the endpoints too early (e.g., within 3 months).

Claims to be verified:

The AFFIX study will verify the following relevant claims related to MaxTack[™]:

- Positive clinical outcomes for fixation of prosthetic material to soft tissue in minimally invasive ventral hernia repair procedures compared to State Of The Art expressed by:
 - the hernia recurrence rate
 - the change in subject Quality of Life (QoL), as measured through the administration o the Hernia Quality of Life Survey (HerQLes) questionnaire (Section 18.4 Appendix D – HerQLes Quality of Life Questionnaire), evaluated at screening and compared to other timepoints
 - the change in subject-reported pain score at the hernia site evaluated with the Numeric Rating Scale (NRS) (Section 18.3 Appendix C – Pain Numerical Rating Scale) at screening compared to other timepoints
- Ability to accommodate physicians in their surgical techniques and clinical cases by enabling prosthetic material fixation to soft tissue: ease of use, compatibility with minimally invasive surgical approach(es) assessed using the Surgeon Satisfaction Questionnaire (Section 18.8 Appendix H – Surgeon Satisfaction Questionnaire).

7. Product Description

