14.7 Handling of Missing Data

The primary analysis will be based on observed data from all subjects enrolled and receiving study devices (full analysis set) with no imputation for missing data. A sensitivity analysis with all possible outcome values for any missing data will be run on the primary endpoint analysis to assess the robustness of the study results. All practical monitoring and follow-up steps will be taken to ensure complete and accurate data collection.

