14.8 Multiplicity Adjustment

Only one hypothesis test is planned. All secondary endpoints will be summarized using descriptive statistics, and no multiplicity adjustment will be considered.

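### Pain and HerQLes change are summarised on available cases only, so the Month 12 estimate can be biased in either direction while earlier scores on file go unused

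*Protocol*

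**What the plan says.** Section 5.2.2 lists two subject-reported secondary endpoints: "Change in subject-reported pain at the hernia site evaluated with Numeric Rating Scale (NRS) score from 0 to 10 at screening" and "Change in subject Quality of life (QoL), as measured through the administration of the Hernia Quality of Life Survey (HerQLes) questionnaire". Each is "evaluated at screening and compared to the following timepoints", namely Months 1, 3 and 12.

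Section 14.5 sets the data behind every secondary summary: "A statistical summary of secondary endpoints will be based on data from the full analysis set for subjects, with non-missing data for each secondary endpoint". Means and, where applicable, 95% confidence intervals are reported on that basis. The next sentence gives recurrence its own rule: "Recurrence endpoints will be based on a previous recurrence or evaluable data at the time point". Pain and HerQLes have no comparable rule.

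Section 14.7 plans one missing-data sensitivity analysis, limited to the primary endpoint: "A sensitivity analysis with all possible outcome values for any missing data will be run on the primary endpoint analysis". Section 14.8 adds: "All secondary endpoints will be summarized using descriptive statistics, and no multiplicity adjustment will be considered".

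Under the claims to be verified, section 6.1 lists the HerQLes change and "the change in subject-reported pain score at the hernia site evaluated with the Numeric Rating Scale (NRS").

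**The concern.** An available-case mean at Month 12 estimates the mean change among subjects who supplied a Month 12 score. It equals the mean for the full analysis set only if those subjects and the missing ones have the same average Month 12 change. Nothing in section 14.5 checks that condition or relaxes it.

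Many subjects missing at Month 12 will already have a screening score and a Month 1 or Month 3 score in the database. Those scores carry information about the missing value, and the stated rule leaves them out. Recurrence and the primary endpoint are handled with more care: recurrence uses earlier information, and the primary endpoint has an analysis over all possible missing outcomes.

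What is at stake is the support for two claims in section 6.1. No test stands behind these endpoints, so the mean change and its interval are themselves the evidence, and any bias passes straight into the claim. The primary conclusion on recurrence is not affected.

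**Working it through.** **Inputs from the protocol**
- About 110 subjects enrolled and 9% attrition within 3 months (synopsis, section 14.6). Check: 100 / (1 − 0.09) = 109.9, about 110; and 110 × 0.91 = 100.1 evaluable. The plan's figure is reproduced.
- No Month 12 missing rate, no standard deviation and no expected change for NRS or HerQLes is given.
- Lost and withdrawn subjects are not replaced (sections 10.14.4, 10.14.5).

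Everything below on size therefore rests on assumptions.

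**Step 1: the identity.** Let *m* be the share missing at a visit and *d* the mean change in observed minus missing subjects. Then

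bias = observed mean − full-set mean = *m* × *d*.

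On the NRS a negative change is an improvement. A negative *d* (missing subjects did worse) therefore flatters the result, a positive *d* understates it, and *d* = 0 gives no bias.

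| Missing, *m* | Absolute bias at a gap of 1 point | at a gap of 3 points |
|---|---|---|
| 9% | 0.09 | 0.27 |
| 20% | 0.20 | 0.60 |
| 30% | 0.30 | 0.90 |

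The same identity holds for HerQLes. For an assumed gap of 10 to 20 score points, the bias is 0.9 to 1.8 points at 9% missing and 2.0 to 4.0 at 20%.

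**Step 2: sampling error for scale.** With an SD of change of 2.5 and 22% lost, the standard error is 2.5 / √(110 × 0.78) = 2.5 / 9.26 = 0.27. Taking instead SDs of 2.2 at screening and 1.8 after surgery, with a screening-to-postoperative correlation of 0.2 to 0.4:
- variance of change = 4.84 + 3.24 − 2ρ × 3.96, which is 6.50 at ρ = 0.2 and 4.91 at ρ = 0.4
- SD of change = 2.55 to 2.22
- standard error = 0.28 to 0.24

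About 0.25 is a fair working value.

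**Step 3: simulated Month 12 bias.** Each trial has 110 subjects. The odds of loss rise 1.5- to 3-fold per SD of the variable driving loss.

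| What drives loss | Lost by Month 12 | Bias in mean NRS change |
|---|---|---|
| Worse earlier change (true mean equal at all visits) | 9–22% | −0.06 to −0.38 (flattering) |
| Higher Month 3 pain level | 9–22% | −0.02 to −0.08 (flattering) |
| Higher screening pain | 9–22% | +0.06 to +0.34 (unfavourable) |

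The screening row has the opposite sign because the endpoint is a change from screening: subjects with high screening pain have the most room to improve, and losing them lowers the apparent benefit. The ranges move with the assumed correlations. With the second SD set in step 2, a postoperative correlation of 0.6 and 22% lost, they are +0.13 to +0.37 for loss driven by screening pain and −0.02 to −0.13 for loss driven by Month 3 level.

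**Step 4: using the scores on file.** In every setting of the step 3 table, a likelihood estimate that uses the earlier scores was within 0.01 of the truth, with an equal or slightly smaller standard error. In all these settings loss depends only on recorded scores, which is the condition under which that estimate is expected to be valid.

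**Step 5: size against error.** 0.02 / 0.25 = 0.08 standard errors; 0.4 / 0.25 = 1.6 standard errors.

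**The case against.** **The SAP may deal with it.** Section 14 calls itself high-level and defers detail to a SAP that is not shown. That document may add a model or a sensitivity analysis. But the available-case basis is a rule the protocol states, and a SAP that follows section 14.5 keeps it as the summary. The point concerns that stated choice.

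**The direction is unknown.** A reader might infer that subjects doing badly drop out, so that Month 12 looks better than it is. The documents do not support this. They say nothing about who is lost, symptom-free subjects may equally skip a late visit, and loss linked to screening pain reverses the sign. Nor does each visit necessarily describe a different group: the subsets differ only as far as data are missing, and each change is measured against the subject's own screening score.

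**Relation to earlier scores is not enough for bias.** Available-case means are biased only if loss is related to the Month 12 change itself. A link to earlier pain matters only through that. This stands, as does the remark that the simulations favour the likelihood estimate by construction. If loss depends on current pain that was never recorded, the model is biased too.

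**Loss may be small.** Remote collection of both scores (section 10.9), use of out-of-window visits (section 10.3) and repeated contact attempts (section 10.14.5) all limit missing data. With loss driven by the Month 3 change and an SD of 2.5, 9% lost gives a shift of only 0.03 to 0.13 points. These measures reduce the problem but do not say how to treat what remains.

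**The endpoints are descriptive.** There is no test or success criterion, and a Month 3 to Month 12 contrast is not an endpoint. That limits the weight of the point but does not remove it, because section 6.1 attaches claims to both changes.

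**Conclusion.** The point holds in a limited form. Section 14.5 fixes an available-case summary for pain and HerQLes change, leaves unused the scores already recorded for subjects lost later, and has no missing-data analysis beside it. If loss is related to the Month 12 change, the mean and its 95% CI can be biased either way. At an assumed 9 to 22% loss by Month 12, the shift is roughly 0.02 to 0.4 NRS points, against a standard error of about 0.25. It can therefore be negligible or larger than the sampling error, depending on a loss pattern the protocol does not describe. The SDs, correlations, loss rates and odds ratios are all assumptions; the only attrition figure in the protocol is 9% by Month 3. The primary endpoint is untouched. The change is worth making because both endpoints support named claims and the better estimate costs little.

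**What to change.** In section 14.5, and in the SAP to match, add one mixed model for repeated measures for NRS change and one for HerQLes change. Use visit as a factor, the screening score as a covariate and an unstructured covariance, and include every subject in the full analysis set with at least one postoperative score. Report the model-based mean changes at Months 1, 3 and 12 with 95% CIs beside the available-case summaries, and give the number missing at each visit.

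The cost is a wording change and one standard model per endpoint. No visit, assessment or subject is added, and precision is about unchanged. The downside is small: the model relies on a missing-at-random assumption, does not correct loss driven by unrecorded later scores, and still omits subjects with no postoperative score.
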